### 7.3 Day 1 Post-TTI-621 infusion (see [Table 7-1](#))

- vital signs at completion of infusion (approximately 60 minutes after Time 0 [ $\pm$  15 minutes]) and 2 and 4 hours after Time 0 [ $\pm$  15 minutes])
- 12-lead ECG within approximately 30 minutes of the completion of infusion (i.e., 60–90 minutes after Time 0)
- Serum for PK:
  - For Part 3: at completion of infusion (approximately 60 minutes after Time 0), 2 hours and 4 hours after Time 0, Day 2 (approximately 24 hours after Time 0). See [Table 7-2](#) and [Appendix D. Table 2](#).
  - For Part 4: at completion of infusion (approximately 60 minutes after Time 0), 2 hours, 4 hours after Time 0, Day 2 (approximately 24 hours after Time 0) and Day 4 (approximately 72 hours after Time 0). See [Table 7-2](#) and [Appendix D. Table 2](#). If a priming regimen is used, see [Appendix F](#) for revised sampling timepoints.
- Hematology:
  - For Part 3: - at completion of infusion (approximately 60 minutes after Time 0), 2 hours, and 4 hours after Time 0 ( $\pm$  15 minutes).
  - For Part 4: at completion of infusion (approximately 60 minutes after Time 0), 2 hours, 4 hours after Time 0 ( $\pm$  15 minutes), Day 2 (approximately 24 hours after Time 0) and Day 4 (approximately 72

hours after Time 0), see [Appendix D. Table 2](#). If a priming dose is used, see [Appendix F](#) for revised sampling timepoints.

- biomarkers ( $\pm$  15 minutes; see Laboratory Manual for details of sample splitting, preparation, and shipping):
  - serum for cytokine/chemokine panel at completion of infusion (approximately 60 minutes after Time 0) and 4 hours after Time 0, (not required for Part 4).
  - whole blood for receptor occupancy at completion of infusion (approximately 60 minutes after Time 0)
- AEs
- concomitant medications

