## 1.7 Anticipated or Possible Risks in Human Subjects

### *Summary of Dose-Escalation Safety Data*

Data from the first 18 subjects enrolled in the dose-escalation phase of the study show that TTI-621 has been reasonably well tolerated. Transient, dose-dependent decreases in platelets without clinical sequelae occurred in the hours following infusion in the majority of subjects exposed to TTI-621. Thrombocytopenia was relatively brief with recovery to baseline platelet counts by the next weekly dose and appeared attenuated with weekly TTI-621 exposure. Other Grade 3/4 cytopenias (monocytes, neutrophils, and lymphocytes) were also frequently observed; all were transient and resolved without sequelae.

The majority of subjects experienced mild to moderate infusion-related reactions (IRRs) that typically occurred after the first TTI-621 infusion only. IRRs were reported across all dose cohorts with no obvious dose relationship and occurred despite premedication with an antihistamine and acetaminophen.

Three subjects experienced reversible Grade 3 hypophosphatemia in the days following their first infusion of TTI-621. Hypophosphatemia in 1 of the 3 subjects was considered related to TTI-621 and was therefore reported as a DLT. The event rapidly resolved without intervention. Hypophosphatemia was considered unrelated to TTI-621 in the other 2 subjects and their phosphate levels were corrected by oral phosphate.

No subjects in either the 0.05 mg/kg/week or 0.1 mg/kg/week dose groups experienced dose-limiting toxicity (DLT). However DLTs were reported for 2 of 5 subjects treated at the 0.3 mg/kg/week dose: 1 subject with Grade 4 thrombocytopenia and 1 subject with Grade 4 thrombocytopenia and Grade 3 elevated alanine aminotransferase/aspartate aminotransferase (ALT/AST). Upon review of cumulative adverse events (AEs) and laboratory values, the Safety Review Committee (SRC) recommended proceeding with

enrollment at an intermediate dose level of 0.2 mg/kg TTI-621 (Cohort 2a), and to dose reduce all subjects participating in the 0.3 mg/kg cohort to the 0.2 mg/kg dose level (one subject was dose reduced to the 0.1 mg/kg dose level).

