### **3.3.3 Definition of Dose-limiting Criteria for Phase 1b Part 4 (Amendment 9)**

Dose-limiting toxicity is defined as any of the following TAEs that occur during the 21-day DLT treatment/observation period (including the pre-dose tests on Day 22/Week 4 Day 1) and that are considered at least possibly related to study treatment by the investigator. Note that any AEs for which the relationship to study treatment cannot be ruled out should be considered possibly related:

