#### Non-hematologic toxicity

- Grade 3 or higher non-hematologic toxicity with the following exceptions:
  - Grade 3 nausea and/or vomiting lasting  $<72$  hours with standard supportive care
  - Transient Grade 3 fatigue lasting  $\leq 72$  hours
  - Transient asymptomatic Grade 3 laboratory abnormalities considered not clinically significant following agreement between investigators and the sponsor's medical monitor and that last  $<72$  hours with standard supportive care
- Other  $\geq$  Grade 2 TTI-621-related non-hematologic toxicities that, in the opinion of the investigator, require a dose reduction or discontinuation of TTI-621

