## 7.2 Day 1 Pre-infusion

For the TTI-621 monotherapy cohorts, the procedures listed below will be performed at the indicated time relative to the infusion of TTI-621. For subjects in the combination cohorts, the procedures below will be performed relative to the infusion of the combination partner. Except where noted, these assessments can be performed up to 24 hours pre-infusion. Baseline testing are assessments preformed within 3 days prior to or on Day 1 pre-dose. Subjects with screening laboratories within 3 days prior to dosing for a particular variable need not repeat the test on Day 1. To proceed with Day 1 infusion, subjects should meet eligibility criteria.

- symptom driven physical examination (as before) and ECOG score
- body weight
- vital signs prior to infusion (performed per the institutional standard of care)
- resting 12-lead ECG within 60 minutes prior to infusion ( $\pm$  30 minutes)
- serum chemistries (as before)
- hematology (as before)
- serum for PK 30 minutes pre-infusion (see [Section 7.14.2](#))
- biomarkers ( $\pm$  15 minutes; see Laboratory Manual for details of sample splitting, preparation, and shipping)
  - serum for cytokine/chemokine panel (not required for Part 4).
  - serum for anti-tumor antibodies (not required for Part 4).
  - whole blood TCR V $\beta$  sequencing (not required for Part 4).
  - whole blood for receptor occupancy

- whole blood for innate and adaptive response assay (not required for Part 4).
- serum for ADA prior to infusion ( $\pm$  15 minutes)
- urinalysis (color, appearance, specific gravity, pH, glucose, bilirubin, ketones, occult blood, protein)
- coagulation for Part 4 only

Subjects in the combination cohorts will also undergo the following additional assessments. These assessments are to be done after the combination partner infusion and prior to the TTI-621 infusion:

- vital signs 60 minutes ( $\pm$  15 minutes) after completion of the combination partner infusion (only if the combination partner and TTI-621 are administered more than 60 minutes apart); performed per the institutional standard of care
- vital signs prior to TTI-621 infusion ; performed per the institutional standard of care

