## 7.6 TTI-621 Intrasubject Dose Intensification – Additional Assessments Every Week of Dose Intensification (only applicable to Part 3)

For subjects who are dose intensified at Week 3 through Week 8, the following assessments are required on Day 1, only if not already part of the scheduled weekly visit. For the TTI-621 monotherapy cohorts, assessments will be performed at the indicated time relative to infusion of TTI-621. For subjects in the combination cohorts, pre-infusion assessments will be performed relative to the start of the combination partner infusion, as applicable.

- serum for PK at end of infusion and 4 hours after Time 0 (see [Table 7-2](#))
- whole blood for receptor occupancy: pre-infusion and at end of infusion (approximately 60 minutes after Time 0,  $\pm$  15 minutes)
- hematology at 4 hours after Time 0. Additional hematologic monitoring should be instituted at the discretion of the treating Investigator.
- serum chemistries at 4 hours after Time 0

## 7.7 Week 4

On Day 1 of Week 4 (Day 22 of treatment), the below tests and observations will be performed. For the TTI-621 monotherapy cohorts, assessments will be performed at the indicated time relative to the infusion of TTI-621. For subjects in the combination cohorts, assessments will be performed relative to the infusion of the combination partner, as applicable. All of these assessments can be performed up to 24 hours pre-infusion, with the exception of vital signs and PK. For Part 3 only, if intrasubject dose intensification occurs at this visit please also refer to [Section 7.6](#) for additional assessments.

- symptom driven physical examination and ECOG score
- body weight
- vital signs prior to infusion and at completion of infusion (60 minutes after Time 0 [ $\pm$  15 minutes]). For subjects in the combination cohorts, the latter timepoint (60 minutes after Time 0) is to be done only if the combination partner and TTI-621 are administered more than 60 minutes apart; performed per the institutional standard of care. For subjects under Part 4 vitals are not required at end of infusion. Refer to [Appendix D. Table 2](#).
- urine or serum pregnancy test for women of childbearing potential
- Serum for PK:
  - For Part 3: serum for PK trough levels (pre-dose)
  - For Part 4: serum for PK trough levels (pre-dose). If a priming regimen is used see [Appendix F](#) for revised sampling timepoints.
- Hematology:

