	WBC with automated 5-part differential, hemoglobin, RBC, absolute reticulocytes, platelets													
Serum chemistries	X	pre	pre	pre	pre				pre	pre Wk 12 then Q4 wks	X	X		
	Alkaline phosphatase, albumin, ALT, AST, bilirubin (direct, indirect, and total), BUN, creatinine, glucose, LDH, total protein, uric acid, and elec troytes (sodium, potassium, calcium, chloride, bicarbonate, phosphorus)													
Coagulation panel	X	pre	pre	pre	pre				pre	pre Wk 12, W16 then Q4 wks p	X			
	Prothrombin time, partial thromboplastin time, INR, fibrinogen													
Urinalysis		pre									X			
	Including color, appearance, specific gravity, pH, glucose, bilirubin, ketones, occult blood, and protein													
D = Day; Post = after start of TTI-621 infusion; EOT = end of treatment visit; SFU = safety follow-up visit; LTFU = long term safety follow-up visit; EOI = end of infusion (1 hr)														

Assessments	$\leq$ -D14	W1 a	W2 D1	W3 D1	W4 D1	W5 D1	W6	W7 D1	W8 D1	W9 + D1	EOT	SFU e	LTFU	
DLT Evaluation Period														
		Except where otherwise noted pre-dose assessments can be performed up to 24 hours pre-infusion (see also Section 7 ). All scheduled treatment days have a window of $\pm 2$ days.										$\leq 1$ Wk h	$\pm 2$ D	Q4 ( $\pm 1$ wk)
Central Laboratory Assessments														
PK o		pre 1 hr (EOI) 2hr, 4hr, D2, D4	pre	pre	pre	pre	pre, 1 hr (EOI) 2 hr, 4 hr D2, D4	pre	pre	pre Wk 9, 10, 11, 12, 13, 14, 15 & 16	X			
ADA		pre			pre				pre	pre Wk 12 then Q4 wks	X	X	X f	
Peripheral Receptor Occupancy (blood) q		pre, 1 hr (EOI)	pre				pre, 1 hr (EOI)	pre		pre Wk 12 and 16				
Tissue for biomarkers r	X								pre	pre Wk 16				

D = Day; Post = after start of TTI-621 infusion; EOT = end of treatment visit; SFU = safety follow-up visit; LTFU = long term safety follow-up visit; O = optional, EOI = end of infusion (1 hr)

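### Part 4 requires no serum chemistry between the first dose and the next weekly visit, so a Grade 3 laboratory DLT can start and resolve unsampled

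*Protocol*

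**What the plan says.** **Blood draws after the first dose.** For Part 4 without priming, Protocol Section 7.3 sets PK at the end of infusion and then at "2 hours, 4 hours after Time 0, Day 2 (approximately 24 hours after Time 0) and Day 4 (approximately 72 hours after Time 0". Hematology has the same times in Section 7.3 and in Appendix D Table 2. With a one-week priming dose, Appendix F moves the Day 2 and Day 4 hematology and PK draws to Week 2, the first full dose.

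**Chemistry.** In Week 1 the panel appears under Section 7.2, pre-infusion, as "serum chemistries (as before". It is absent from the post-infusion list in Section 7.3, from Table 7-1 and from Appendix F. The Appendix D Table 2 row begins "Serum chemistries X pre pre pre pre", that is, screening and then pre-dose at Weeks 1, 2, 3 and 4. Section 7.1 shows that the panel includes phosphorus, ALT, AST and bilirubin.

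**DLT rule.** Section 3.3.3 sets a 21-day window, "including the pre-dose tests on Day 22/Week 4 Day 1". Related non-hematologic toxicity of Grade 3 or higher counts. One exception covers "Transient asymptomatic Grade 3 laboratory abnormalities considered not clinically significant following agreement between investigators and the sponsor's medical monitor", provided that the abnormality lasts less than 72 hours with supportive care.

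**Phase 1a experience.** Section 1.7 reports: "Three subjects experienced reversible Grade 3 hypophosphatemia in the days following their first infusion of TTI-621". One of the three cases was judged related and was a DLT; it cleared quickly with no treatment. It was the only DLT among the six evaluable subjects at 0.2 mg/kg. At 0.3 mg/kg, one subject's DLT combined Grade 4 thrombocytopenia with Grade 3 ALT/AST elevation.

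**The concern.** Part 4 re-estimates the MTD from the number of DLTs per dose level. A chemistry abnormality without symptoms can enter that count only if blood is drawn while it is present. The protocol brings patients back on Day 2 and Day 4 after the first dose and takes blood, but asks for no chemistry from those draws. The trial's own early data place one kind of chemistry DLT in exactly that part of the week.

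The revised rule also depends on duration: under 72 hours can be exempt, 72 hours or more cannot. The Table 6-1 footnote requires repeat testing before the next visit to settle the 72-hour question, but only for Grade 4 thrombocytopenia, Grade 4 neutropenia and Grade 3 febrile neutropenia, and only by hematology. For other toxicities, Section 6.5.3 asks for re-evaluation at least weekly once a dose is withheld, which is too coarse to separate under 72 hours from longer. At stake are the completeness of the DLT count and the ability to apply the exception as written.

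**Working it through.** The documents state no figure on this point, so there is none to reproduce. The check compares the schedules and works out the interval without chemistry.

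**1. Required draws after the first unprimed dose and before the Week 2 pre-dose draw**

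| Test | End of infusion | 2 h | 4 h | Day 2 | Day 4 | Total |
|---|---|---|---|---|---|---|
| Hematology | yes | yes | yes | yes | yes | 5 |
| PK | yes | yes | yes | yes | yes | 5 |
| Serum chemistry | no | no | no | no | no | 0 |

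**2. Time T from the first infusion to the next required chemistry**

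- The next infusion is nominally at day 7 after the first. Section 7 allows plus or minus 2 days from Week 2 onward, so days 5 to 9.
- Section 7.4 lets Week 2 assessments be done up to 24 hours before the infusion. Chemistry is not among the exceptions.
- Nominal: T = 7 − 1 to 7, so 6 to 7 days.
- With the visit window: T = 5 − 1 to 9, so 4 to 9 days.

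**3. When a countable event escapes every required draw**

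Let o be the onset in days after the dose and d the duration at Grade 3. The event is outside the laboratory exception on duration if d ≥ 3, and it is unsampled if o + d < T. For an event of exactly 72 hours, onset must therefore come before T − 3:

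- T = 4: before day 1
- T = 6: before day 3
- T = 7: before day 4
- T = 9: before day 6

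At the nominal schedule, an event starting on day 1 can last up to T − 1 = 5 to 6 days and still be over before the next required chemistry.

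**4. An event first seen on Day 8**

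The last earlier chemistry was before the first dose, so onset may lie anywhere in the preceding 6 to 7 days. Whether the event has lasted less than 72 hours cannot be established from the required samples.

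**5. Priming cohorts**

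Appendix F covers hematology, PK and receptor occupancy only. Chemistry stays pre-dose, so the same gap of nominally 6 to 7 days follows the first full dose in Week 2.

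**6. What Day 2 and Day 4 chemistry would add, at nominal times (days 1 and 3 after the dose)**

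- Onset by day 1, d ≥ 3: still present at the day 1 or day 3 draw.
- Onset after day 1 and by day 3, d ≥ 3: present at the day 3 draw.
- Onset after day 3: can still escape if it comes before T − 3, that is, between days 3 and 4 when T = 7, and not at all when T = 6.
- For an event first seen on Day 8 after a normal Day 4 result, onset is narrowed to the preceding T − 3 = 3 to 4 days.

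**The case against.** The strongest reply is that few events would both be missed and count.

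- **Exempt or unrelated events.** The phase 1a hypophosphatemia DLT cleared quickly. If it was asymptomatic, shorter than 72 hours and agreed not to matter clinically, Part 4 would exempt it. The other two Grade 3 cases were judged unrelated. This stands as a limit on the example. The protocol gives no duration for the DLT case, and an exemption still requires that the event be seen and timed.
- **Other routes of detection.** AEs are recorded from the first dose, investigators may order extra tests, Section 9.5 asks for close liver-enzyme monitoring, and the SRC weighs all safety data, including later and cumulative toxicity. This also stands. It confines the gap to asymptomatic events for which nobody orders an unscheduled test, so it would be wrong to say that such events are never recorded.
- **ALT/AST.** No onset or duration is given for the ALT/AST event, and that subject also had Grade 4 thrombocytopenia. The events-in-between pattern is documented for hypophosphatemia only; for transaminases it is a possibility under the schedule.
- **Rarity.** Section 9.5 reports Grade 3–4 ALT/AST increases in 3 of 179 subjects. Hypophosphatemia is not among the commoner related events of Grade 3 or higher in Section 1.7, where all unlisted events occurred in at most 2 subjects. These counts come largely from lower doses and similar sampling and may understate, but they do not support a high chemistry DLT rate.

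None of these points supplies a required chemistry sample in the gap.

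**Conclusion.** The gap is real. In Part 4 there are about 6 to 7 days (4 to 9 with windows) after the first dose with five required post-dose hematology draws and no required chemistry, and the same gap follows the first full dose under priming. A related asymptomatic Grade 3 chemistry abnormality of 72 hours or more can start and finish within it, and the laboratory exception cannot be timed for one first found on Day 8. This rests on the schedule as written and on no unscheduled test being ordered.

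Three stronger readings go beyond the documents:

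- **A missed fraction, or a changed escalation probability.** A reader might assume an onset and duration and carry the missed share through the 3+3 rule. No durations are given, and the answer follows the assumptions. With a true DLT rate of 30% and 40% of chemistry DLTs missed (both assumed), P(escalate) = (1−p)³ + 3p(1−p)⁵ rises from 0.49 to 0.75 if every DLT is a chemistry event (p = 0.30 × 0.60 = 0.18), but only to 0.52 if chemistry contributes 3 of the 30 points (p = 0.30 − 0.03 × 0.40 = 0.288). Neither is an estimate for this trial.
- **A DLT count biased low overall.** Missed events lower the count. An abnormality seen on Day 8 that cannot be shown to be exempt would, read literally, remain a DLT and raise it. The net direction is not established.
- **Closer sampling in Part 3.** Section 7.6 adds "serum chemistries at 4 hours after Time 0", but only in intensification weeks from Week 3. Part 3 also has no post-dose chemistry after the first infusion, and a 4-hour sample would not catch events that arise over the following days.

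**What to change.** Add the serum chemistry panel to the Day 2 and Day 4 draws already scheduled after the first Part 4 dose, and to the same draws after the first full dose in Appendix F. Update Section 7.3, Table 7-1, Appendix D Table 2 and Appendix F together so that they agree.

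The cost is one extra local tube at two existing draws, with no new visit, and a few more laboratory abnormalities to adjudicate. The change narrows the gap after that one dose. It leaves the intervals after the other doses in the DLT window as they are, and it improves the timing of the 72-hour exception without settling it in every case.

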**Table 7-1: Week 1 Temporal Summary of Infusion and Post-infusion Assessments**

	T = 0 min	T + 60 min	T + 2 hr	T + 4 hr	T + 24 hr	T + 72 hr
Start TTI-621 infusion		Start infusion [Timeline: T = 0 to T + 60 min]	End infusion			
		- - - - - Monitor for infusion reactions - - - - -				
		Vital signs	Vital signs	Vital signs		
		ECG				
		Receptor occupancy				
		Pharmacokin.	Pharmacokin.	Pharmacokin.	Pharmacokin.	Pharmacokin. (Part 4 only)
		Hematology	Hematology	Hematology	Hematology	Hematology (Part 4 only)
		Cytokines/chemokines (Part 3 only)		Cytokines/chemokines (Part 3 only)		

## 7.4 Week 2

On Day 1 of Week 2 (Day 8 of treatment), the below tests and observations will be performed. For the TTI-621 monotherapy cohorts, assessments will be performed at the indicated time relative to the infusion of TTI-621. For subjects in the combination cohorts, assessments will be performed relative to the infusion of the combination partner, as applicable. All of these assessments can be performed up to 24 hours pre-infusion, with the exception of vital signs, PK, and biomarkers. Post-infusion procedures will be relative to the TTI-621 infusion.

- symptom-driven physical examination and ECOG score
- body weight
- vital signs prior to infusion and at completion of infusion (60 minutes after Time 0 [ $\pm$  15 minutes]). For subjects in the combination cohorts, the latter timepoint (60 minutes after Time 0) is to be done only if the combination partner and TTI-621 are administered more than 60 minutes apart; performed per the institutional standard of care. For subjects under Part 4, vitals are not required at end of infusion. Refer to [Appendix D. Table 2](#).
- biomarkers ( $\pm$  15 minutes; see Study Manual for details of sample splitting, preparation, and shipping):
  - serum for cytokine/chemokine panel (pre-dose), not required for Part 4
  - whole blood for receptor occupancy (pre-dose) for Part 3 and 4. For Part 4, if a priming dose is used see [Appendix F](#) for revised sampling timepoints.
- Serum for PK:
  - For Part 3 and Part 4: serum for PK trough levels (pre-dose). See [Appendix D. Table 1](#) and [Appendix D. Table 2](#). If a priming regimen is used, see [Appendix F](#) for revised sampling timepoints.
- Hematology:
  - For Part 3: pre-dose (results must be available prior to start of infusion). Further hematologic monitoring should be instituted at the discretion of the treating Investigator.
  - For Part 4: pre-dose (results must be available prior to start of infusion) and 4 hours after Time 0 ( $\pm$  15 minutes). Day 2 (approximately 24 hours after Time 0) assessments are required if clinically indicated, in the event that  $\geq$  Grade 4 thrombocytopenia is observed on day 1 or there are any other clinical conditions indicated for a follow-up lab at the investigator discretion. Further hematologic monitoring should be instituted at the discretion of the treating

Investigator. If a priming dose is used, see [Appendix F](#) for revised sampling timepoints.

- serum chemistries
- AEs
- concomitant medications
- coagulation panel only for Part 4

## 7.5 Week 3

On Day 1 of Week 3 (Day 15 of treatment), the below tests and observations will be performed. For the TTI-621 monotherapy cohorts, assessments will be performed at the indicated time relative to the infusion of TTI-621. For subjects in the combination cohorts, assessments will be performed relative to the infusion of the combination partner, as applicable. All of these assessments can be performed up to 24 hours pre-infusion, with the exception of PK and vital signs. For Part 3 only, if intrasubject dose intensification occurs at this visit please also refer to [Section 7.6](#) for additional assessments.

- symptom driven physical examination and ECOG score
- body weight
- vital signs prior to infusion and at completion of infusion (60 minutes after Time 0) [ $\pm 15$  minutes]. For subjects in the combination cohorts, the latter timepoint (60 minutes after Time 0) is to be done only if the combination partner and TTI-621 are administered more than 60 minutes apart; performed per the institutional standard of care. For subjects under Part 4, vitals are not required at end of infusion. Refer to [Appendix D, Table 2](#).
- Serum for PK:
  - For Part 3: serum for PK trough levels (pre-dose)
  - For Part 4: serum for PK trough levels (pre-dose). If a priming dose is used see [Appendix F](#) for revised sampling timepoints.
- Hematology:
  - For Part 3: pre-dose (results must be available prior to start of infusion). Further hematologic monitoring should be instituted at the discretion of the treating Investigator.
  - For Part 4: pre-dose (results must be available prior to start of infusion) and 4 hours after Time 0 ( $\pm 15$  minutes). Day 2 (approximately 24 hours after Time 0) assessments are required if clinically indicated, in the event that  $\geq$  Grade 4 thrombocytopenia is observed on day 1 or there are any other clinical conditions indicated for a follow-up lab at the investigator discretion. Further hematologic

monitoring should be instituted at the discretion of the treating Investigator. If a priming dose is used, see [Appendix F](#) for revised sampling timepoints.

- serum chemistries
- AEs
- concomitant medications
- coagulation panel only for Part 4
- biomarkers ( $\pm$  15 minutes; see Study Manual for details of sample splitting, preparation, and shipping):
  - For Part 4: If a priming dose is used additional whole blood for receptor occupancy is required. See [Appendix F](#) for additional sampling timepoints.

